11.3 Randomisation

The aim of this pilot study is to test the concept of a novel cot/safe sleep enabler in the maternity unit in the first instance. The availability of the MaBim Neonatal Cot will be limited to 4 cots (due to costs) and the First Days Pēpi-Pod® will be limited to 15 cots for this pilot. All beds will have a standard cot available.

This study intends to provide information to inform the development of a protocol for a randomised controlled trial. The pilot protocol will include a trial of the randomisation process to be used in the larger trial as staff education relating to processes used in the pilot have been considered. Introducing differences in the randomisation process to accommodate the unequal number of intervention cots was considered problematic; particularly as feasibility of the protocol was a key outcome of the pilot. The following methodology for randomisation has been adopted based on the intentions of the pilot within the resource limitations of limited numbers of First Day the pilot study, and is believed to be workable given the average length of stay of mothers in this maternity unit.

On arrival to the postnatal unit, participants will be randomised to one of three options; ‘The First Days Pēpi-Pod®’, ‘The MaBim Neonatal Cot’ or a standard bedside cot. The midwife will take the next sealed, opaque envelope located on a box of envelopes, in a locked cabinet, in the midwives’ work station. The midwife in charge of the shift will hold the key for the cabinet. Inside the envelope will either be a label stating, ‘The First Days Pēpi-Pod®’, ‘The MaBim Neonatal Cot’ or standard bedside cot. This randomisation label will then be placed on the postnatal pathway. The midwife in charge will make an entry in the Project Register (held in locked cabinet with sealed envelopes) of participant name, envelope number and cot allocation.

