If the allocated cot is not available (i.e. the First Days Pepi-Pod® or MaBim are already in use) the participant will be allocated to a standard cot. These allocations will be managed as a fourth group in the analysis in which demographic information should theoretically be similar to the standard cot allocated group. This method also serves as an internal checking procedure for the randomisation process used in the clinical environment. In this instance, the midwife in charge will make an entry in the Project Register for participant name, envelope number, first cot allocation, non-availability and reallocation to standard cot and will place the envelope into the discard box (to allow checking of integrity of the randomisation process).

A total of 300 envelopes will be prepared representing each of the three options equally (100/100/100) and which will also allow for the envelope discard process. A mock run of the randomisation process indicated that based on an estimated 7 deliveries per day and an average stay of 3 days, the four MaBim cots would be in almost constant use and approximately half of those mother-baby pairs randomised to the MaBim would be allocated

to use them. This process will allow integrity of the randomisation of process while still maintaining recruitment for each target sample within a feasible timeframe.

An allocation to a cot is intended for the duration of hospitalisation. The usual length of hospital stay for a woman having a vaginal delivery is 1-3 days; for a woman delivering by caesarean section 3-5 days. Analyses will be by Intention to Treat according to actual allocation and Actual Use, consistent with a recent randomised controlled study of safe sleep enabler use (Baddock et al., 2017).

The study will continue until there is a minimum of 60 participants in each group (total n=180) and will allow an attrition rate of up to 50% during the 4 month follow-up period following discharge from the post-natal unit. The final target sample for this pilot is 30 participants in each group with a complete data set.

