12.2 Data analysis

Data collection and analyses will include maternal and infant demographics; breastfeeding outcomes (at discharge, 6-8 weeks and 4 months); length of stay; maternal-infant attachment; maternal satisfaction and perceptions relating to enabler use; staff time to recruit and educate families, perceptions relating to intervention impact and adverse events; and maternal and

staff awareness of safe sleep recommendations (self reported and observed). Data from this pilot, the first Australian trial of a hospital postnatal safe sleep enabler, will be used to inform a randomised controlled trial of safe sleep enablers in postnatal environments.

Maternal Data: Analysis of maternal data will be conducted using the principles of intention to treat. All participants who were enrolled and randomly allocated to treatment are included in the analysis and will be analysed in the groups to which they were randomised. A further analysis will be based on actual use, consistent with a recent published study on Wahakura use, a Maori safe sleep enabler, intended for domestic use after discharge home to the community (Baddock et al., 2017) which performed analyses based on intention to treat and actual use.

Statistical analyses will be performed to report the prevalence and proportions of variables surveyed. Questionnaire results will be entered into a purpose-built Microsoft Excel database for data cleaning and preparation for statistical analysis. A 10% random selection (approximately 9-10 questionnaires from each of the maternal records, staff survey and audits) will be double entered to assess data-entry accuracy and intra-rater reliability. Consistency checks will be performed on all variables to ensure that only valid responses will form the basis of the ensuing analysis.

Quantitative data will be analysed using descriptive techniques such as frequency and percentage and measures of central tendency and distribution (for example, mean and standard deviation or median and IQR). Normality of data will be assessed. Group comparisons to comparing equivalency of control and interventions will be conducted with Chi-squared test for categorical measures and analysis of variance or Kruskal-Wallis test for continuous measures as appropriate assessing for normality and equality of variances.

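### The protocol gives two unreconciled rules for mothers whose allocated device was in use (a fourth analysis group, or the arm randomised), and the fourth-group rule would remove mothers almost only from the MaBim arm

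*Protocol*

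**What the plan says.** **Section 11.3, Randomisation.** On arrival at the postnatal unit, "participants will be randomised to one of three options": First Days Pēpi-Pod, MaBim or standard cot, with 100 envelopes for each. Supply of the MaBim is "limited to 4 cots (due to costs) and the First Days Pēpi-Pod® will be limited to 15 cots for this pilot". When the device drawn is already in use, "the participant will be allocated to a standard cot", and for the analysis: "These allocations will be managed as a fourth group in the analysis". The section adds that this group should resemble the standard-cot group demographically and treats that as an internal check on randomisation. The Project Register records the first allocation, the non-availability and the reallocation, and the used envelope is kept. The section then states: "Analyses will be by Intention to Treat according to actual allocation and Actual Use".

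**Section 12.2, Data analysis.** "Analysis of maternal data will be conducted using the principles of intention to treat"; everyone randomised is included, and participants "will be analysed in the groups to which they were randomised". A further analysis by actual use follows.

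**The concern.** A mother who drew a MaBim envelope but received a standard cot is in the MaBim arm under section 12.2 and in a separate group under section 11.3. For any one comparison she cannot be in both. The sentence on intention to treat in 11.3 does not settle the matter, because the register holds two allocations for her and the sentence does not say which one is meant.

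The choice matters because membership of the fourth group depends on whether a device was free, not on the draw alone. Taking those mothers out leaves a MaBim group made up only of mothers who arrived when a MaBim was free, set against standard-cot mothers who arrived at any time. Secondary hypotheses 3 to 5 (section 5.2) and the group tests in section 12.2 call for comparisons between enabler users and standard-cot mothers on satisfaction, attachment, breastfeeding, safe-sleep awareness and length of stay. The rule also decides whose acceptability answers count as MaBim answers. Section 11.3 says the pilot tries out the randomisation process for the larger trial, so an unclear rule could carry forward.

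**Working it through.** **1. The protocol's own figure.** Section 11.3 reports a mock run with 7 deliveries per day and a 3-day stay: the four MaBim cots almost always in use, and about half of MaBim-randomised pairs receiving one.

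- MaBim demand = 7 × 1/3 = 2.33 per day; offered load a = 2.33 × 3 = 7.
- Erlang loss formula: B(0) = 1, then B(k) = a·B(k−1) / (k + a·B(k−1)).
- With a = 7: B(1) = 0.875, B(2) = 0.754, B(3) = 0.638, B(4) = 0.527. So 52.7% find no MaBim free and 47.3% receive one; cot use = 7 × 0.473 / 4 = 83%.
- A day-by-day simulation (7 arrivals a day, fixed 3-day stay) gives 46% not served and 94% cot use.

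Both results agree with the protocol's figure.

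**2. The same calculation at the trial's recruitment rate.** Seven deliveries a day is close to all births (2800 / 365 = 7.7 per day). Only participants draw envelopes. Section 12.1 gives 30-40 eligible births per week and 40% participation, so 12-16 participants per week. The 3-day stay is carried over as an assumption.

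| Participants per week | Load (rate / 7 × 1/3 × 3 days) | No MaBim free |
|---|---|---|
| 12 | 1.71 | 6.7% |
| 16 | 2.29 | 12.6% |

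For stays of 2 to 4 days the range is 2% to 21%.

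**3. Which arms lose mothers.** With 15 Pēpi-Pods and a load of 7, B(15) = 0.3%; at the trial's rate it is effectively zero. The standard arm cannot lose anyone.

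| Arm | Mock-run load | Section 12.1 rate, 3-day stay |
|---|---|---|
| MaBim | about 50% (46-53%) | about 7-13% |
| Pēpi-Pod | about 0.3% | about 0% |
| Standard | 0 | 0 |

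Per 60 mothers randomised to MaBim, that is about 30 at the protocol's half, or 4 to 8 at the section 12.1 rate (60 × 0.067 = 4.0; 60 × 0.126 = 7.6).

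**4. Keeping everyone in the arm drawn.** If mothers without the device get no effect from it, the as-randomised difference is the true difference × (1 − share not served). A true 10-point difference becomes about 5 points at one half, and 8.7 to 9.3 points at 7-13%.

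**5. How far MaBim availability tracks a busy ward.** I simulated constant-rate Poisson arrivals of 7 births per day with a mean 3-day stay (about 21 mothers on the ward). The mean number of mothers on the ward at admission was lower for MaBim recipients than for the standard arm by about 0.2-0.4 at 12-16 participants per week, and by about 1.0-1.2 when every mother takes part. Seasonal or staffing changes are not modelled.

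**6. The demographic check.** It compares the fourth group with the standard arm. It never compares the remaining MaBim mothers with the standard arm, which is the contrast affected. A difference could also reflect when mothers arrived rather than a fault in randomisation.

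**The case against.** The strongest reply is that two analyses are planned, as randomised and by actual use. Section 12.2, the dedicated analysis section, states the first plainly. A reallocated mother could stay in her arm for intention to treat and appear separately under actual use, and the sentence in 11.3 can be read as naming both analyses. That is a workable reading and probably the best one. But no sentence confines the fourth group to actual use, so an analyst following 11.3 literally would take these mothers out.

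A reader might infer that MaBim versus standard is confounded by ward workload. The documents do not show this. Reallocation is triggered by four cots being held by earlier MaBim draws on a unit of about 50 beds, which depends largely on the envelope order and on lengths of stay. Step 5 suggests only a weak link with how full the ward is. What is lost is the guarantee that randomisation gives; bias has not been demonstrated.

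A reader might also infer that both device comparisons are damaged, or that half of the MaBim arm will go. Pēpi-Pod is hardly touched, and the half assumes that nearly every birth enters the trial.

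Two further points stand. This is a pilot whose primary outcomes are acceptability and feasibility, and acceptability is naturally described among users. The register and the retained envelopes do allow an audit of the allocation process, even though the demographic comparison does not do that job.

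**Conclusion.** The two sections give different analysis groups for the same mothers, and the protocol does not say which rule governs. This rests on the text alone and holds whatever the reallocation rate.

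If the fourth group is used in the main comparison, the loss is one-sided: MaBim about 7-13% at the recruitment rate in section 12.1 (assuming a 3-day stay and steady arrivals) and about half at the mock-run rate; Pēpi-Pod about 0.3% at most; standard none. MaBim versus standard, and MaBim versus Pēpi-Pod, would then not compare randomised groups. The direction and size of any resulting bias are unknown, and it may be modest. The documents do not support a claim that the two rules could never coexist, or that the results would be confounded. They support the narrower conclusion that the rule has to be settled before analysis.

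**What to change.** 1. **State one intention-to-treat rule** in sections 11.3 and 12.2: three groups defined by the envelope drawn, with reallocated mothers kept in the arm drawn. Reword the reference to actual allocation in 11.3 to match 12.2. This needs no new data, because the register already holds the first allocation.
2. **Limit the fourth group** to description or the actual-use analysis, and report the number of reallocations as a feasibility result. Do not present the demographic comparison as a test of randomisation; rely on the register and the retained envelopes for that audit.
3. **Record in the Project Register, before each envelope is opened, whether a MaBim is free**, including for mothers who go on to draw a standard cot. At present non-availability is noted only when the device drawn is unavailable. Because availability is then fixed before the draw, a supplementary MaBim versus standard comparison limited to mothers randomised while one was free stays randomised and is not diluted by non-availability.

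Items 1 and 2 cost only wording. Item 3 costs one register field, and the supplementary comparison is smaller: MaBim and standard mothers drawn while no MaBim was free both leave it. That is about 4 to 8 of every 60 in each of the two arms at 7-13%, and about 30 of 60 if the mock-run half applies. It should therefore supplement the three-group analysis and not replace it.

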5. HYPOTHESES

5.1 Primary Hypotheses

The priority of the pilot is to test the novel concept of safe sleep enablers for the first time in an Australian setting. Two primary hypotheses will focus on maternal acceptability of the safe sleep enablers as alternative infant sleep spaces and the feasibility of the proposed protocol in a busy maternity setting.

The primary hypotheses are:

1. Acceptability with infant safe sleep enablers will be demonstrated by mothers in the maternity unit setting.
2. Feasibility of a pilot protocol to evaluate safe sleep enablers in the maternity unit setting will be demonstrated (as measured by staff support, appropriate application of the protocol: consent, randomisation, documentation processes).

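### Demographic similarity of the reallocated fourth group is weak evidence that randomisation was followed; the full envelope sequence should be the main check

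*Protocol*

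**What the plan says.** Section 11.3 of the protocol describes allocation on the postnatal ward. "The midwife will take the next sealed, opaque envelope" from a locked cabinet whose key is held by the midwife in charge, who enters "participant name, envelope number and cot allocation" in the Project Register for each participant.

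If the drawn device is already in use, the mother receives a standard cot and joins a fourth group in the analysis. Of that group the protocol says that "demographic information should theoretically be similar to the standard cot allocated group", and then: "This method also serves as an internal checking procedure for the randomisation process used in the clinical environment". For these mothers the register also takes "envelope number, first cot allocation, non-availability and reallocation to standard cot", and the midwife in charge "will place the envelope into the discard box (to allow checking of integrity of the randomisation process").

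Section 5.1 makes randomisation part of the second primary hypothesis, on feasibility, which is measured by staff support and "appropriate application of the protocol: consent, randomisation, documentation processes". Section 12.2 gives the general comparison methods: "Group comparisons to comparing equivalency of control and interventions will be conducted with Chi-squared test" for categorical measures, and analysis of variance or Kruskal-Wallis for continuous ones. No test, margin or pass rule is attached to the fourth-group comparison.

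**The concern.** Section 11.3 gives a checking role to the resemblance of two groups. Three features weaken it.

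- **Size.** The fourth group exists only when devices run out, and only the four MaBim cots are likely to. At the recruitment that section 12.1 expects, this happens seldom.
- **Direction.** Envelopes are opened on the ward by midwives. One obvious breach is to pass over an envelope in order to steer a mother to a device, and that requires a free device. The fourth group arises when the device is not free, so it carries little trace of such a breach.
- **Inference.** No margin is stated, and the tests in section 12.2 are tests of difference. A non-significant result in a handful of mothers does not show similarity, and similarity does not show that the sequence was kept.

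At stake is a primary feasibility outcome. Section 11.3 says that the pilot tries out the randomisation process meant for the larger trial, so a reassuring result from a weak check could carry an unnoticed fault forward.

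**Working it through.** **Inputs.** From section 11.3: 4 MaBim cots, 15 Pēpi-Pods, 300 envelopes in three equal parts, a mock run at 7 deliveries per day with a 3-day stay, and recruitment to at least 60 per group. From section 12.1: 30-40 eligible births per week and 40% participation. Assumptions: a 3-day mean stay throughout, two-sided 0.05, and 0.5 SD as an illustrative baseline difference (the protocol names none).

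**Formula.** With c cots and load a = (randomised per day) × 1/3 × (stay in days), the Erlang loss formula gives the share of device draws that find no cot free:

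B = (a^c / c!) / Σ(k = 0 to c) a^k / k!

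**Step 1: reproduce the mock run.** a = 7 × 1/3 × 3 = 7 and c = 4, so B = 100.04 / 189.71 = 52.7%. Then 47.3% of those drawing a MaBim receive one, which matches the protocol's figure of about half. For the 15 Pēpi-Pods B = 0.3%, so the fourth group is almost entirely MaBim draws. Of 100 MaBim envelopes about 53 would be reallocated; simulation with the same 300 envelopes gave about 46-48.

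**Step 2: use the recruitment rate in section 12.1.** 30 × 0.40 = 12 and 40 × 0.40 = 16 randomised per week, against 7 × 7 = 49 in the mock run.

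| Randomised per week | Load a | B | MaBim draws needed for 60 users, 60/(1 − B) | Reallocated |
|---|---|---|---|---|
| 12 | 12/7 = 1.71 | 0.360/5.383 = 6.7% | 64.3 | 4.3 |
| 16 | 16/7 = 2.29 | 1.137/9.026 = 12.6% | 68.7 | 8.7 |

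A simulation with stays of 1-3 days (vaginal) and 3-5 days (caesarean), stopping at 60 per group, gave means of 3.1 and 6.5. The range is therefore about 3-9 mothers.

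**Step 3: chance of missing 0.5 SD.** Two-sample t-test with non-centrality 0.5 / √(1/n₄ + 1/n_S), where n₄ is the fourth group and n_S the standard-cot group:

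| Fourth group v standard | Non-centrality | Missed |
|---|---|---|
| 3 v 60 | 0.85 | 87% |
| 6 v 60 | 1.17 | 79% |
| 9 v 60 | 1.40 | 72% |
| 47 v 100 (mock-run rate) | 2.83 | 20% |
| 53 v 100 (mock-run rate) | 2.94 | 17% |

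**Step 4: simulated breaches.** These used an assumed caesarean share of 30% or 35% and assumed breach patterns. None of these is a figure from the protocol, so only the direction should be relied on. Entries are the share of simulated trials with p < 0.05; ranges span several simulation runs.

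| Breach | Rate | Fourth v standard | By first label drawn |
|---|---|---|---|
| Skipping envelopes to steer caesarean mothers to a device | 12-16 per week | 6-21% | 71-99% |
| Same | mock run | 14-36% | 54-87% |
| Falsely declaring MaBim unavailable (in one run, for half of vaginal births) | 12-16 per week | 93-99% | 4-7% |
| Same | mock run | 36% | 5% |

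Skipping left about 11-22 envelopes out of sequence, which the register's envelope numbers would show directly. False unavailability swelled the fourth group to about 36-38 mothers at 12-16 per week, which is why the fourth-group comparison sees it there.

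**The case against.** The strongest reply is that the protocol does not rest on demographics alone. The sentence says that the method also serves as a check, and the method may be read as the whole procedure of reallocating and recording. The next sentence keeps the envelope for checking integrity, and every participant's envelope number is registered. This stands: the documentary trail exists and is the better instrument. But the discard box receives only the envelopes of reallocated mothers, so a skipped envelope need not enter it, and no section plans to reconcile the full sequence.

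A second reply is that the size depends on the load. This also stands: at the mock-run rate the comparison has about 80% power for 0.5 SD. That rate, however, randomises every delivery, whereas section 12.1 allows for eligibility and 40% participation, a rate it calls conservative.

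A third reply is that the comparison is sensitive to one breach that the first-label comparison misses, namely false declarations of non-availability. This stands, and it is a reason to keep the comparison.

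A reader might infer that randomisation would be declared sound whatever happened, or that the section 12.2 tests are the pass rule. The documents support neither. No decision rule is stated, and section 12.2 speaks of control and interventions without naming this comparison or randomisation integrity.

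**Conclusion.** The point holds as a weakness in how randomisation is to be checked. It does not show that the randomisation is unsound or unmonitored. At 12-16 randomised per week, resemblance between about 3-9 reallocated mothers and 60 standard-cot mothers says little: a 0.5-SD difference is missed 72-87% of the time, and envelope skipping would seldom show. If 7 per day were truly randomised, the group would be about 50 and the miss rate about 17-20%.

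The group sizes rest on the protocol's own rates and an assumed 3-day mean stay. The breach detection rates rest on assumed breaches and serve only to show that the two comparisons see different faults.

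It is tempting to conclude that the fourth-group comparison should be deleted. The working does not support that, because it is the comparison that responds to misuse of the reallocation step. Nor do the documents say that this comparison decides whether the envelope process goes into the larger trial; it is one input to a primary feasibility outcome. The change is a cheap improvement.

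**What to change.** In section 11.3:

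1. State that similarity of the fourth group to the standard-cot group, or a non-significant difference between them, is not evidence that randomisation was followed.
2. Make the main integrity measure a reconciliation of all 300 numbered envelopes, not only those in the discard box, against the Project Register and the prepared allocation list. Report the number and proportion used out of sequence, missing, opened without a participant, or carrying a label that differs from the list, with an exact 95% confidence interval.
3. Tabulate baseline data by first label drawn.
4. Keep the fourth-group comparison as a descriptive audit of reallocations, and check each logged non-availability against the cots recorded as in use at that time.

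The cost is a few sentences, a date and time added to each register entry, and a short reconciliation at study end. Envelope numbers and allocations are already recorded.

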5.2 Secondary Hypotheses

This study has several secondary hypotheses, due to the need to pilot a protocol and identify key outcomes for a larger, randomised controlled trial. Secondary hypotheses include:

1. Maternal satisfaction with infant safe sleep enablers will be demonstrated by mothers in the maternity unit setting.
2. Staff who use the infant safe sleep enablers will find infant safe sleep enablers acceptable to use in practice in the maternity unit setting.
3. Mothers who use a safe sleep enabler for their infant in the postnatal unit will report higher levels of satisfaction with care, maternal-infant attachment outcomes, breastfeeding rates, and safe sleeping awareness during the postnatal period (≥ 3 days and 6-8 weeks) compared to mothers who use the current standard cot and separate maternal bed.
4. Mothers who use a safe sleep enabler for their infant in the postnatal unit will report higher breastfeeding rates and safe sleeping awareness at 4 months postnatal age compared to mothers who use the current standard cot and separate maternal bed.
5. Mothers who use a safe sleep enabler for their infant in the postnatal unit will report the same or reduced length of hospital stay, and the same or lower rate of adverse events including baby falls during hospitalisation.
6. Compared to pretest knowledge, attitudes and self reported practices, staff will demonstrate an improvement in knowledge, attitudes and self reported practices consistent with current safe sleeping recommendations and known risk factors at the conclusion of the pilot period.
7. Compared to pretest audits of infant sleep position, environment and documentation of parent education, there will be an improvement in practices and documentation processes consistent with current safe sleeping recommendations and known risk factors at the conclusion of the pilot period.

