Once the mother has birthed, she will be randomly allocated on admission to the postnatal unit to the MaBim side-car crib, First Days Pēpi-Pod® or control (usual care with baby sleep space being independent hospital Perspex cot on wheels) during the postnatal stay.

All participants will be shown the Video Clip titled 'Safe, Sleep, Little One' (CFOC Ltd, 2016) by the midwife once orientated to the ward. If allocated to the First Days Pēpi-Pod, participants will also be asked to view the Picture Demonstration (CFOC Ltd, 2016). Participants allocated to the MaBim neonatal crib will be shown the MaBim Product Brochure. Those randomised to the control group (usual cot care) will receive standard care instructions.

Participants will be followed up by the Research Assistant during the hospital admission to assess breastfeeding rates, acceptability of the ISSD or control, maternal-infant attachment, maternal satisfaction with the care received, culturally appropriate care, accessibility of personal options and choice in care, adverse events (baby falls from maternal beds or chairs) and awareness of, and compliance with, safe sleeping recommendations. Participants will be asked to complete the questionnaires, expected to take thirty minutes of the participants' time. The participant will be given the choice to complete the questionnaires independently or have the Research Assistant read the questions. The questionnaire will be available online (Opinio Survey Software 7.1) and in paper format.

If participants discharge prior to contact with the Research Assistant, she will be contacted within seventy-two hours of discharge, or at the next time of convenience.

Prior to discharge, participants will be asked to view the 'Red Nose Safe Sleeping' information (SIDS and Kids Australia, 2016) available via the mobile phone application. This information video promotes safe sleeping practices in the home environment.

Infant sleep observation and maternal chart audits for participating mothers and babies will be conducted (using the audit tools described in Phase 1) prior to discharge.

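### Length of stay is compared without adjusting for mode of birth, a strong predictor fixed before randomisation, so the comparison is valid but less precise than it need be

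*Protocol*

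**What the plan says.** Section 11.3 of the protocol states: "The usual length of hospital stay for a woman having a vaginal delivery is 1-3 days" and, "for a woman delivering by caesarean section 3-5 days". Section 12.1 repeats both ranges. The two meet only at day 3.

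Allocation follows birth. Section 11.3: "On arrival to the postnatal unit, participants will be randomised to one of three options". Section 11.5.1: "Once the mother has birthed, she will be randomly allocated on admission to the postnatal unit". The envelopes are split equally over the three cots, and no stratification by mode of birth is described.

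Length of stay is a secondary outcome in 10.2. Secondary hypothesis 5 in 5.2 says that mothers using an enabler "will report the same or reduced length of hospital stay".

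For maternal group comparisons, 12.2 names the chi-squared test for categorical measures and "analysis of variance or Kruskal-Wallis test for continuous measures". No covariate is mentioned. Logistic, log-linear and linear models appear in 12.2 only for the staff survey and audit data. Maternal data are to be analysed by randomised group and again by the cot actually used.

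**The concern.** When a variable known before allocation separates the outcome this clearly, an analysis that ignores it treats the gap between modes as noise. Here the midpoints of the usual ranges are two days apart, while any device effect on stay is likely to be a fraction of a day. A chance difference in caesarean share between groups also moves the raw difference directly: at a two-day gap, each 10 percentage points shifts it by 0.2 day.

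What is at stake is how much the pilot can say about hypothesis 5, and how good a description of length of stay it passes to the larger trial (objective 4 in 4.1). The actual-use analysis raises a different issue. Randomisation does not protect it, and sections 9.5 and 9.7 link caesarean birth to discomfort with, or benefit from, particular cots. Mode of birth could therefore influence both which cot is used and how long the mother stays.

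**Working it through.** **Group size for this outcome.** Section 11.3 aims for 30 per group with full data after up to 50% attrition: 30 / (1 - 0.5) = 60 per group, 180 in all, which reproduces the protocol's figure. That attrition falls after discharge, and length of stay is known at discharge, so 60 per group is the relevant number.

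**Inputs from the protocol.** Usual stay 1-3 days (vaginal) and 3-5 days (caesarean), 11.3.

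**Assumptions.**
- Mean stays are the midpoints, 2 and 4 days.
- The caesarean share p is not given; 20-50% is used. The mock run in 11.3 was "based on an estimated 7 deliveries per day and an average stay of 3 days". With these midpoints a 3-day mean implies p = (3 - 2) / (4 - 2) = 50%, so the range includes that value.
- The within-mode SD, s, is not given. It depends on how much of the distribution a usual range covers, so several readings are shown.
- Intervals are two-sided 95%.

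**Formulas.**
- Unadjusted variance = s² + p(1 - p) × (4 - 2)²
- Variance adjusted for mode of birth = s²
- Width ratio = √(unadjusted / adjusted)
- Half-width for two groups of 60 = 1.96 × SD × √(2/60)

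**Worked case** (stays uniform within range, p = 30%):
- s = 2/√12 = 0.577, so s² = 0.333.
- Between-mode variance = 0.3 × 0.7 × 4 = 0.84.
- Unadjusted SD = √1.173 = 1.083; ratio = 1.083 / 0.577 = 1.88.
- Half-widths: 1.96 × 1.083 × 0.1826 = 0.39 day, against 1.96 × 0.577 × 0.1826 = 0.21 day.

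**Width ratio, unadjusted to adjusted.**

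| Reading of the usual range | s (days) | p = 20% | p = 30% | p = 50% |
|---|---|---|---|---|
| Mean ± 2 SD | 0.50 | 1.89 | 2.09 | 2.24 |
| Uniform over the range | 0.58 | 1.71 | 1.88 | 2.00 |
| Holds 90% of stays | 0.61 | 1.65 | 1.81 | 1.93 |
| Mean ± 1 SD (about two thirds) | 1.00 | 1.28 | 1.36 | 1.41 |
| Interquartile range (half) | 1.48 | 1.14 | 1.18 | 1.21 |

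**Half-widths at 60 per group, p = 30%.** Uniform: 0.39 against 0.21 day. SD 1.0: 0.49 against 0.36 day. Interquartile reading: 0.62 against 0.53 day.

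**Share of variance due to mode of birth**, 1 - 1/ratio², over p = 20-50%: 0.66-0.80 for s = 0.50-0.58, 0.39-0.50 for s = 1.0, and 0.23-0.31 for s = 1.48.

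**Check by simulation.** A linear model on three groups of 60, fitted with and without mode of birth, gave mean ratios at p = 30% and 50% of 2.08 and 2.24 (s = 0.50), 1.87 and 2.00 (uniform), 1.36 and 1.41 (s = 1.0), and 1.17 and 1.20 (s = 1.48). These agree with the formula.

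**Chance imbalance at 60 per group.** Over p = 20-50%, two groups differ in caesarean share by at least 20 points with probability of about 1-4%, and by at least 10 points with probability of about 21-32%.

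**The case against.** The strongest reply is that nothing here is invalid. Randomisation makes the unadjusted comparison unbiased, the study is a descriptive pilot, length of stay is one of many secondary outcomes tested at a nominal level, and covariates are often settled in a statistical analysis plan. Most of this stands: the issue is precision on one outcome, and it changes no acceptability or feasibility conclusion. The last part stands only in part. Section 12.2 does choose the maternal tests, so this is a stated method with a better alternative at hand. If an unseen analysis plan already adjusts for mode of birth, the point falls away.

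A second reply is that 12.2 plans tests and summaries, not an interval, and allows Kruskal-Wallis for non-normal data. That is correct. The half-widths above describe the precision of a mean difference; they do not describe the rank test. Still, part of any non-normality in pooled stays would come from mixing the two modes, which the adjusted model removes.

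Three stronger readings are tempting, and the document does not support them:
- A reader might infer that the unadjusted interval is about twice as wide as needed, or that mode of birth explains most of the variance. Both need a within-mode SD of about 0.5-0.6 day, that is, usual ranges holding about 90% or more of stays. The protocol says only that these stays are usual.
- A reader might take 30 per group as the sample and conclude that large caesarean imbalances are likely. Thirty is the full-data target after post-discharge attrition. Section 12.1 does speak of recruiting 90, but also of 90 with complete datasets after 50% attrition. The width ratio does not depend on group size in any case.
- A reader might extend the loss to feeding, attachment and satisfaction. The protocol gives no figure for how these vary with mode of birth.

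**Conclusion.** The point holds as a matter of precision. By the protocol's own ranges mode of birth strongly predicts length of stay, it is fixed before allocation, and the stated maternal comparisons do not use it. Adjustment narrows the length-of-stay interval under every reading examined, but by how much cannot be fixed from the document: a factor of about 1.1 to 2.2 overall, near 2 only if the usual ranges contain nearly all stays. Even at a within-mode SD of 1.0 day, the gain equals that from 1.6-2.0 times the sample (1.28² to 1.41²).

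These figures rest on mean stays of 2 and 4 days and a caesarean share of 20-50%, neither of which the protocol states. The intention-to-treat comparison is not biased. In the actual-use comparison mode of birth is a plausible confounder, and the reason to adjust there is validity as well as precision.

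**What to change.** In 12.2, state that length of stay will be analysed with a linear model containing randomised group and mode of birth (vaginal or caesarean), and that the adjusted device-minus-standard difference will be reported with a 95% CI for each device. Include mode of birth in the actual-use analysis of length of stay as well. Leave the envelope process unchanged.

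Adjusting the other maternal outcomes is optional, because the document gives no basis for the size of any gain.

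The cost is a sentence or two of analysis text, one degree of freedom and one covariate. Table 1 in 11.4 already draws maternal and neonatal data from the Client Health Record after birth. Mode of birth is not named there, so it should be added to the items extracted.
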